5 STUDY POPULATION

5.1 Participant Inclusion Criteria

To be eligible to participate in this study, an individual must meet all of the following criteria:

- Is a current limited or full participation member of the Network (EQ Qx 7).
- Practice includes non-implant restorative dentistry (Responds occasionally or routinely to EQ Qx 21).
- Is a practicing dentist or dental therapist in the US (EQ Qx 1: response categories 1-10 or 12).
- For non-VA/CHC dentists, has verified EQ contact information on file since 1-2020at which he or she can be contacted (EQ contact information).
- Responds to the first item of the study questionnaire that in a typical month, they treat 1 or more adult patients (18+ years) who have at least one deep carious lesion in a posterior tooth, that extends into the inner 1/3 of the dentine.

5.2 Strategies for Recruitment and Retention

Recruitment

As of mid-June 2020, 7,859 members were enrolled in the National PBRN. Of this total, 0.03% are dentists providing care in public health clinics, community health centers and VA dental services, while 45.9% are dentists providing care in other practice types. We will actively recruit new dentists and dental therapists from public health clinics, community health centers and VA dental services to join the Network as practitioners within these practice types treat patients with a higher prevalence and incidence of dental caries.

The study population will include a stratified random sample. A census of eligible Network dentists and dental therapists practicing in public health clinics, community health centers and VA dental services will be taken. A random sample of eligible Network dentists and dental therapists from other dental practice types will be invited to participate, using a randomized denominator file. A minimum sample size of 385 respondents will be obtained. Meetings will be held with Regional Node Coordinators to review recruitment issues and enrollment progress.

Compensation

Participants who wish to receive compensation and are able to accept payment will be remunerated \$50 for completing the electronic questionnaire. If participants complete the test-retest of the electronic questionnaire, they will be remunerated an additional \$50. Payment will be sent to participants following the conclusion of each of the waves of the study.

5.3 Participant Withdrawal

5.3.1 Reasons for Participant Withdrawal

Participants can choose not to participate in the study and are free to withdraw, i.e., not complete the questionnaire, at any time without penalty.

5.3.2 Handling of Participant Withdrawals

It is anticipated that participants will not be replaced since the invitation numbers are based on prior Network recruitment experience.

5.4 Premature Termination or Suspension of Study

This study may be suspended or prematurely terminated if there is sufficient reasonable cause. The PI is responsible for promptly notifying all parties and providing the reason(s) for the termination or suspension.

Circumstances that may warrant termination include, but are not limited to:

- Insufficient adherence to protocol requirements.
- Data that are not sufficiently complete and/or evaluable.
- Determination of futility.

6 STUDY SCHEDULE

6.1 Phase 1 – Enrollment of New Practitioners into the Network

- Dentists practicing in public health clinics, community health centers, and VA dental service clinics will be encouraged to enroll into the Network.
- Dentists in these practice settings tend to treat patients with a higher prevalence and incidence of dental caries and are therefore suited to answer the study questionnaire regarding deep carious lesion treatment strategies.

6.2 Phase 2, Part A – Recruitment of Practitioners into the Study

- Eligible dentists and dental therapists will be identified from responses to the Network Enrollment Questionnaire and will be invited to participate based on inclusion criteria.
- A stratified random sample will be taken. A census of Network dentists and dental
 therapists practicing in public health clinics, community health centers and VA dental
 services will be taken. A random sample of eligible dentists and dental therapists
 from other dental practice types will be invited to participate, using a randomized
 denominator file.
- Agreement to complete the questionnaire will indicate that study participants have read the consent information, and this will imply tacit consent. A waiver of signed consent will be requested from the IRB.

Phase 2, Part B- Retest of the Questionnaire

- Dentists and dental therapists selected from among those study participants who completed the questionnaire will be emailed a second online questionnaire request approximately two weeks after the receipt of their first completed questionnaire.
- Dentists and dental therapists will be informed they have approximately two weeks
 to respond to the invitation to complete the retest. If the retest is not completed
 within the approximate two-week time frame, the link to the retest questionnaire will
 be disabled. A new potential retest participant will be selected from those having
 already completed the questionnaire until a total of approximately 40 retests have
 been completed.
- Completion of the retest questionnaire will indicate implied consent.

6.3 Phase 3 – Merging Study Questionnaire with Enrollment Questionnaire and Completion of Data Analyses

- Study questionnaire and Network enrollment questionnaire data will be linked using participant IDs.
- Contact information will be removed from the final merged dataset and data will be stored/saved using Unique Participant IDs.
- Data Analyses will be completed as described in Section 11.3 Final Analysis Plan.

7 STUDY PROCEDURES/EVALUATIONS

Questionnaire Development

The study questionnaire was developed by the study team, and contains questions adapted from the United Kingdom's SCRIPT trial and previous Network studies. The questionnaire has undergone review by the NCC to ensure it is psychometrically sound and to ensure the data it collects will allow for adequate evaluation of study objectives. Further, cognitive testing of the questionnaire was completed, in which dentists reviewed their responses to a completed survey and were probed to assess possible respondent problems in understanding questions, recalling necessary information, and/or reporting accurately.

Questionnaire User Testing

The NCC will perform internal testing of the electronic study questionnaire, including internet browser compatibility. Study team members (e.g. SPI, National Network Director, Regional Directors, etc.) will be given the opportunity to externally test the website prior to administration to study participants.

Questionnaire Administration

According to the inclusion criteria, eligible participants, i.e., Network dentists and dental therapists whose practice includes non-implant restorative dentistry will be identified from their responses to the Network's enrollment questionnaire.

Consistent with regulations outlined by the University of Alabama IRB and regional/local IRBs, information about the study will be provided to all eligible participants via an information sheet/questionnaire link in the email invitation.

After the initial invitation and follow-up email reminders, the NCs will systematically contact non-responders, and participants with incomplete information, by email, phone, or fax to encourage questionnaire completion. If no feedback is received or the participant does not complete the questionnaire after these follow-up attempts, it will be assumed the practitioner is not interested in the study. Node Coordinators may also contact participants as part of data cleaning conducted by the NCC.

8 ASSESSMENT OF SAFETY

8.1 Definitions of Safety Parameters

8.1.1 Unanticipated Problems

The Office for Human Research Protections (OHRP) considers unanticipated problems involving risks to subjects or others to include, in general, any incident, experience, or outcome that meets all of the following criteria:

- unexpected in terms of nature, severity, or frequency given (a) the research procedures that are described in the protocol-related documents, such as the IRBapproved research protocol and informed consent document; and (b) the characteristics of the subject population being studied;
- related or possibly related to participation in the research (possibly related means there is a reasonable possibility that the incident, experience, or outcome may have been caused by the procedures involved in the research); and
- suggests that the research places subjects or others at a greater risk of harm (including physical, psychological, economic, or social harm) than was previously known or recognized.

8.2 Specification of Safety Parameters

Safety monitoring for this study will focus on unanticipated problems involving risks to participants.

8.3 Reporting Procedures

8.3.1 Unanticipated Problem Reporting

Per Network procedures, unanticipated incidents and events will be reported to the PI. After the PI is made aware of the incident/event, the following procedures will be followed.

Incidents or events that meet the OHRP criteria for unanticipated problems require the creation and completion of an unanticipated problem report form. OHRP recommends that investigators include the following information when reporting an adverse event, or any other incident, experience, or outcome as an unanticipated problem to the IRB:

- appropriate identifying information for the research protocol, such as the title, investigator's name, and the IRB project number;
- a detailed description of the adverse event, incident, experience, or outcome;

- an explanation of the basis for determining that the adverse event, incident, experience, or outcome represents an unanticipated problem;
- a description of any changes to the protocol or other corrective actions that have been taken or are proposed in response to the unanticipated problem.

To satisfy the requirement for prompt reporting, unanticipated problems will be reported using the following timeline:

- Unanticipated problems will be reported to the IRB as soon as possible but in all cases within 10 working days of the investigator becoming aware of the problem.
- All unanticipated problems should be reported to appropriate institutional officials (as required by an institution's written reporting procedures), the supporting agency head (or designee), and OHRP within one month of the IRB's receipt of the report of the problem from the investigator.

All unanticipated problems will be reported to NIDCR concurrently with reporting to the IRB. These reports will be made to NIDCR's centralized reporting system via the Clinical Research Operations and Management Support (CROMS) contractor:

- Product Safety Fax Line (US): [name]
- Product Safety Fax Line (International): [contact]
- Product Safety Email: rho [contact]

9 STUDY OVERSIGHT

The PI will be responsible for study oversight, including monitoring safety, ensuring that the study is conducted according to the protocol and ensuring data integrity. The NCC will provide the PI with current data summaries, and the PI will review the data for safety concerns and data trends at regular intervals, and will promptly submit reportable events to the IRB and NIDCR that arise during the conduct of the study, per the IRB's reporting time-frame requirements. To ensure data integrity, the PI, NCC, and study team will adhere to data quality management processes (please see Section 13).

DCRS-Protocol-2021-02-22-V2.0 Page 17 of 29

10 CLINICAL SITE MONITORING

No outside clinical site monitoring will be employed for this study. The NCC is responsible for launching the study and collecting data received as part of the study. Quality Assurance/Quality Control activities associated with data collection and processing will be outlined in the Data Management Plan. The NCC will ensure that the quality and integrity of the study data and data collection are maintained. The NIDCR reserves the right to conduct independent clinical site monitoring as necessary.

11 STATISTICAL CONSIDERATIONS

11.1 Study Hypotheses

This is a cross-sectional questionnaire of Network dentists and dental therapists assessing their treatment practices regarding the management of deep carious lesions. As such, formal hypothesis testing will not be conducted to achieve the study objectives.

11.2 Sample Size Considerations

The primary aim of the study is descriptive (i.e., to estimate the level of concordance with national guidelines in the sample overall as well as in selected subgroups). As such, sample size calculations are based on the precision with which we can estimate guideline concordance. To a good approximation, if W is the width of the 95% confidence interval (i.e., the confidence interval is of the form $P \pm W/2$) for an estimated proportion P based on N observations, then the N needed to achieve that width is given by

$$N = 16*P*(1-P) / (W^2)$$
,

where P and W are expressed on a fractional basis. Thus, a proportion of 20% corresponds to P=0.20, and if the width of the conf interval were 10 percentage points then W would be 0.10. For a given value of W, the formula above is symmetric about P=0.5 and is largest for P=0.5. Hence using P=0.5 above will give a conservative value of N that assures a width \leq W regardless of the value of P.

The target N of 385 chosen for this study will enable us to estimate proportions for the population as a whole with a precision (95% confidence interval) of no greater than \pm 5 percentage points, \pm 7.1 percentage points for subgroups of size N/2, \pm 8.7 percentage points for subgroups of size N/3, and \pm 10 percentage points for subgroups of size N/4.

11.3 Final Analysis Plan

Primary Objective: Determine the extent to which, for permanent posterior teeth with deep occlusal caries extending to the inner 1/3 of dentin, Network dentists and dental therapists use caries removal strategies that are in concordance with the recommendations of the ICCC.

The primary analysis will be descriptive in nature. The source data for this analysis will be the proportion of the time dentists and dental therapists say they remove all caries at the periphery of the cavity and stop before the pulp is exposed ("selective caries removal"), which will be assessed separately for patients with symptomatic caries and for patients with asymptomatic caries. For each of these two subgroups, we will describe this as a continuous measure using either means and standard deviations (SD) or, if the data are markedly skewed, medians and interquartile ranges.

We will also calculate the percentage of dentists who are "concordant" with guidelines by dichotomizing this measure. Since there is no universally agreed upon definition for how to define concordance based on such data, we plan to use a variety of cut points to document the extent to which concordance varies with the choice of threshold used to define concordance. These cut points will range from a high of selective caries removal 75% of the time, which we feel is a reasonable measure of good concordance, to a low of selective caries removal 25% of the time to allow for comparison with some previous reports in the literature (15,21,22).

As a secondary analysis, we will use logistic regression analysis to determine the extent to which concordance varies according to selected provider characteristics. For the purposes of this analysis, we will define concordance using our upper end threshold of selective caries removal 75% of the time. We will initially look at all candidate variables in a univariate manner and will use those significant based on these analyses to conduct a reverse stepwise multiple logistic regression analysis. As before, separate analyses will be done for patients with symptomatic caries and for patients with asymptomatic caries.

An additional secondary analysis related to this objective will be to assess the relative importance of various factors when making clinical decisions about management of deep carious lesions. Each factor will be graded on a 5-point Likert scale and simple descriptive statistics will be used to summarize the information.

Secondary Objective: Determine the ability and willingness of Network dentists and dental therapists to participate in a randomized clinical trial evaluating outcomes of selective *versus* non-selective (complete) caries removal for deep lesions in permanent teeth in adults (18+ years).

Simple descriptive statistics will be computed as appropriate for data collected from the study questionnaire. The decision whether a clinical trial is warranted will be determined by the proportion of dentists willing to participate in a clinical trial; their ability to recruit the eligible patients for the trial; and their current use of selective caries removal. The thresholds for the decision whether to proceed with a clinical trial are still to be determined.

Missing data. Data from incomplete questionnaires may be included in data analyses. Depending on the extent of missing data and available resources for analyses, the study team may consider statistically appropriate methods for imputing missing information.

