4 STUDY DESIGN

This study is a cross-sectional questionnaire of Network dentists and dental therapists practicing in public health clinics, community health centers, VA dental services and other dental practice types across the United States. These practice types were chosen as they are more likely to treat patients with a higher prevalence and incidence of dental caries.

The study population will include a stratified random sample. A census of eligible Network dentists and dental therapists practicing in public health clinics, community health centers and VA dental services will be taken. A random sample of eligible Network dentists and dental therapists from other dental practice types will be invited to participate, using a randomized denominator file. At the end of the first wave of recruitment the study team will review the response rate based on EQ practitioner criteria, and may refine the sampling approach for wave 2 recruitment at that time. A minimum sample size of 385 respondents will be obtained.

Eligible Network dentists and dental therapists as described in the previous paragraph will be sent an email invitation to participate in the questionnaire study. This may be done in two or more waves depending on the numbers of eligible participants and on the response rate. The questionnaire will take approximately 15 minutes to complete and will be administered using the Electronic Data Capture System (EDC) on the Network HUB website, housed at the Network Coordinating Center (NCC).

Following the launch of the questionnaire, approximately 40 of the initial survey responders will be selected to complete the electronic questionnaire again (approximately 2 weeks post initial questionnaire completion) to establish test-retest reliability.

Approximately 3 months are estimated to complete recruitment into the study to obtain the desired sample size.

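### The design has unequal selection probabilities, but the ±5-point precision claim assumes a simple random sample and the planned summaries are neither weighted nor reported by sampling stratum

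*Protocol*

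**What the plan says.** **Sampling.** Protocol section 4 (also the Protocol Summary and sections 5.2 and 6.2) sets two strata with different rules. For the first: "A census of eligible Network dentists and dental therapists practicing in public health clinics, community health centers and VA dental services will be taken". For the second: "A random sample of eligible Network dentists and dental therapists from other dental practice types will be invited to participate". No sampling fraction is given for the second. Sections 5.2 and 6.1 plan to enlarge the first stratum by targeted enrollment into the Network. Section 4 allows the sampling approach to be changed for wave 2 after the wave 1 response rate has been reviewed.

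**Precision.** Section 11.2 bases the sample size on "if W is the width of the 95% confidence interval" for a single proportion, takes P = 0.5 as the conservative case, and says that 385 respondents "will enable us to estimate proportions for the population as a whole" to within ±5 points. The same section words the aim differently: "to estimate the level of concordance with national guidelines in the sample overall as well as in selected subgroups".

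**Analysis.** Section 11.3 describes the share of the time that selective removal is used: "For each of these two subgroups, we will describe this as a continuous measure using either means and standard deviations (SD", or medians and interquartile ranges if skewed. The two subgroups in that sentence are symptomatic and asymptomatic caries, not the sampling strata. The percentage concordant is then calculated at several cut points. Willingness and ability to join a trial get simple descriptive statistics. Section 11.3 mentions no weights, no results by sampling stratum and no design-based interval.

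**The concern.** Members of the census stratum are invited with probability 1, and the others with an unstated probability that may change between waves. A pooled mean or percentage then reflects the mix of respondents, which need not match the mix in the Network. If the strata differ in concordance, willingness or ability to recruit, the pooled figure moves toward the census stratum, and more respondents in the same mix do not correct it.

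The precision claim is affected on either route. Without weights, ±5 points is not the error for the Network population when the strata differ. With weights, unequal weighting widens the interval, so 385 respondents no longer give ±5 at P = 0.5.

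Section 11.3 rests the decision on a future trial on three quantities: the proportion willing, the ability to recruit, and current use of selective removal. As written, all three would be pooled figures. The census settings were singled out because their patients have more caries, which bears most directly on ability to recruit.

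**Working it through.** **1. Reproduce the plan's figure.** N = z²·P(1−P)/(W/2)², with z = 1.96, P = 0.5 and W = 0.10, gives 3.8415 × 0.25 / 0.0025 = 384.1, rounded up to 385. The half-widths at 385, 385/2, 385/3 and 385/4 are 4.99, 7.06, 8.65 and 9.99 points, which match section 11.2. (The printed constant of 16 corresponds to z = 2 and gives 400; 385 needs z = 1.96.) No design effect enters, so all four figures assume a simple random sample.

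**2. Inputs.**
- Network size: 7,859 (section 5.2).
- Other practice types: 45.9% × 7,859 = 3,607 dentists, before the remaining eligibility criteria.
- Census stratum as printed: 0.03% × 7,859 = 2.4 dentists, before Phase 1 enrollment.
- Not in the documents, so assumed: census stratum after Phase 1 of 100, 236 (3% of 7,859), 400 or 600; response in that stratum of 30% or 50% (for 600, 190 respondents, about 32%); total respondents 385; difference between strata of 10 points.

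**3. Formulas.** A is the census stratum and B the others; N_A and N_B are members, n_A and n_B respondents.
- Bias of the pooled figure = (n_A/385 − N_A/(N_A + N_B)) × stratum difference.
- Weights to stratum size: w_A = N_A/n_A and w_B = N_B/n_B.
- Kish design effect = 385 × (n_A·w_A² + n_B·w_B²) / (N_A + N_B)².
- Weighted half-width = 4.99 × √(design effect), without finite population correction. Respondents needed for ±5 = 385 × design effect.

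**4. One case in full.** N_A = 236 and 50% response, so n_A = 118 and n_B = 267.
- Population share 236/3,843 = 0.0614; respondent share 118/385 = 0.3065. Bias = (0.3065 − 0.0614) × 10 = 2.45 points.
- w_A = 2.00 and w_B = 3,607/267 = 13.51. Design effect = 385 × (118 × 4.00 + 267 × 182.5)/3,843² = 1.28.
- Half-width 4.99 × √1.28 = ±5.7; respondents needed about 494.

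**5. Range.**

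| Census stratum | Respondents from it | Bias per 10-point difference | Design effect | Weighted half-width | N for ±5 |
|---|---|---|---|---|---|
| 2.4 (as printed) | all | 0.05 | 1.005 | ±5.0 | 387 |
| 100 | 30 (30%) | 0.5 | 1.04 | ±5.1 | 399 |
| 100 | 50 (50%) | 1.0 | 1.09 | ±5.2 | 421 |
| 236 | 71 (30%) | 1.2 | 1.10 | ±5.2 | 423 |
| 236 | 118 (50%) | 2.5 | 1.28 | ±5.7 | 494 |
| 400 | 120 (30%) | 2.1 | 1.21 | ±5.5 | 466 |
| 400 | 200 (50%) | 4.2 | 1.71 | ±6.5 | 657 |
| 600 | 190 (32%) | 3.5 | 1.49 | ±6.1 | 575 |

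The bias scales with the stratum difference: it doubles at 20 points and is zero if the strata do not differ. It is also zero if all of the other stratum is invited and both strata respond equally.

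**The case against.** A reader might infer that the protocol prescribes an unweighted analysis and that its primary estimate is therefore biased. The documents do not go that far.

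- **Weighting is not ruled out.** Section 11.3 never says unweighted, and weights could be set in an analysis plan that is not shown; section 15.3 defers report content to a separate procedure. This stands as far as it goes. Against it, section 6.3 makes section 11.3 the plan to be followed, and the whole-population ±5 in section 11.2 is a statement in the protocol itself that a later weighting rule would contradict.
- **The target is worded inconsistently.** Section 11.2 also refers to the sample, and sections 3.1 and 3.2 refer to participating practitioners. The Protocol Summary refers to eligible practitioners and section 11.3 to Network practitioners. This stands: if respondents are the target, no weighting is needed, but the whole-population claim must go.
- **The size rests on assumptions.** On the printed 0.03% the bias is trivial. No sampling fraction, response rate or stratum difference is stated, and with low response most of the other stratum might be invited. The 3,607 precedes eligibility, and the verified-contact criterion in section 5.1 applies only to dentists outside VA and community health centers; if it shrinks that stratum more, the bias falls. Larger figures need stronger conditions: 4.3 points per 10 with 236 members requires 190 respondents, about 80% response. All of this stands.
- **No difference in concordance is predicted.** Section 2.2 links conservative care to settings with guidelines available, but does not say that the census settings are of that kind. This also stands; a stratum difference is plausible, not documented.

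**Conclusion.** The point holds as a mismatch within the protocol. The design has unequal selection probabilities, the precision statement assumes equal ones and claims the whole population, and the analysis section provides neither weights nor results by stratum. Pooled figures for concordance, willingness and ability would lean toward the census stratum if the strata differ and the other stratum is either not fully invited or responds at a different rate.

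The documents do not determine how far. The lean is about 0.05 points or less per 10-point difference on the printed 0.03%, and about 0.5 to 4 points for an assumed census stratum of 100 to 600 with 385 respondents and 3,607 others. In the assumed cases shown, the lean exceeds the stated ±5 only with a stratum difference larger than 10 points. The loss of precision under weighting does not depend on a stratum difference: about ±5.1 to ±6.5 instead of ±5 for an assumed census stratum of 100 to 400.

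That the primary estimate is biased as a matter of fact is not supported. That ±5 for the population is assured by 385 respondents under this design is not supported either.

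**What to change.** **Section 11.2.** State whether the target is the eligible Network population or the respondents. For the population, restate the precision for 385 with a design effect under stated stratum sizes and response rates, or say that ±5 holds only for a simple random sample.

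**Section 11.3.** Report concordance, willingness and ability by sampling stratum. Give overall population estimates weighted to the eligible Network stratum sizes, using the selection probability by stratum and wave adjusted for stratum response, with stratified design-based 95% intervals. Show the unweighted figures alongside.

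Selection weights alone are not enough. If 95 of 236 census members respond and all 3,607 others are invited, with 290 responding, every selection weight is 1, yet the pooled figure is still off by (0.247 − 0.061) × 10 = 1.9 points per 10-point difference. The response adjustment removes this part.

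**Section 4 and the denominator file.** State the sampling fraction for the other stratum, and record each invitee's stratum, wave and selection probability when invitations are drawn. This is best settled before recruitment, because wave 2 changes are hard to reconstruct afterwards.

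**Cost.** A few sentences and the recorded sampling variables, with no new questionnaire data. The overall interval becomes wider, possibly by more than a little. Keeping ±5 under weighting would take about 399 to 657 respondents across the assumed census strata of 100 to 400.

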There is global disparity in the management of deep carious lesions. A survey of dentists in France, Germany and Norway found that 84% of Norwegian dentists employed the more conservative stepwise removal of dental caries from deep lesions, while the majority of French and German dentists (>66%) performed complete caries excavation, even for deep lesions (8). A nationwide survey (9) of US general dentists, pediatric dentists and endodontists showed that most endodontists (68%) and general dentists (47%) practiced complete caries removal, while pediatric dentists (31%) were more likely than both general dentists (12%) and endodontists (4%) to employ partial caries removal. A systematic review of seven randomized controlled trials comparing selective *versus* non-selective caries removal in children and adolescents found the risk of pulpal exposure significantly reduced in the selective caries removal group (OR=0.11, 95% CI: 0.04-0.30); while no significant difference in pulpal symptoms (OR=0.79, 95% CI: 0.30-2.12) and failure (technical or biological complications needing intervention) (OR=1.40, 95% CI: 0.69-2.84) was found between the two groups (10).

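### The provider-characteristic regression rests on a single 75% cut of a percentage scale, although the protocol says no cut is agreed and varies it everywhere else

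*Protocol*

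**What the plan says.** Section 11.3 starts from a self-reported percentage: "The source data for this analysis will be the proportion of the time dentists and dental therapists say they remove all caries" in the selective manner. The percentage is summarised as continuous (mean and SD, or median and interquartile range if skewed), separately for symptomatic and asymptomatic caries.

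The section then turns to a yes/no classification. It concedes that "there is no universally agreed upon definition for how to define concordance based on such data", and responds sensibly: "we plan to use a variety of cut points to document the extent to which concordance varies with the choice of threshold". The range runs from 75%, "which we feel is a reasonable measure of good concordance", down to 25%, which is included for comparison with earlier reports.

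The next paragraph moves to associations: "As a secondary analysis, we will use logistic regression analysis to determine the extent to which concordance varies according to selected provider characteristics". Here only one definition is used: "we will define concordance using our upper end threshold of selective caries removal 75% of the time". Candidate variables are tested one at a time, and those found significant go into a backward stepwise model. This is done twice, once per symptom group. The section names no regression at another cut and none on the percentage scale.

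**The concern.** The protocol treats dependence on the threshold as a problem for the prevalence of concordance, but not for its correlates. In the regression a practitioner who reports 70% is coded the same as one who reports 0%, and one at 75% the same as one at 100%.

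Two things are at stake. First, precision: splitting a graded measure discards information, and more of it the fewer practitioners lie on one side of the cut. Because entry to the multivariable model requires univariate significance, lost information becomes lost variables. Second, interpretation: a characteristic linked to concordance at 75% need not be linked to it at 50% or 25%, and the planned output would not show this.

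**Working it through.** **The plan's own figure.** Section 11.2 sizes the study on precision. With z = 1.96, P = 0.5 and half-width 0.05, N = 1.96² × 0.25 / 0.05² = 384.15, so 385. Half-widths 1.96 × √(0.25/n) for N, N/2, N/3 and N/4 are 4.99, 7.06, 8.65 and 9.99 points, matching the stated 5, 7.1, 8.7 and 10. (The printed formula, with 16 in place of 4 × 1.96², gives 400; the protocol calls it an approximation.) These figures concern descriptive proportions. Nothing in section 11.2 sizes the regression.

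**Inputs.** From the protocol: N = 385, a percentage outcome, a 75% cut. Not in the protocol, so assumed: the share p above the cut (5% to 50%), the shape of the distribution, two equal provider groups (192 each), two-sided 5% tests.

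**Information kept by one cut.** If the outcome reflects a normal latent tendency and c is the point exceeded by a share p, the efficiency of the split relative to a linear analysis is φ(c)² / [p(1 − p)]. For p = 0.12: c = 1.175, φ(c) = 0.200, so 0.0400 / 0.1056 = 0.379.

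| Share above 75% (assumed) | Kept | Lost | Effective n of 385 | Respondents above cut |
|---|---|---|---|---|
| 50% | 0.637 | 36% | 245 | 192 |
| 25% | 0.539 | 46% | 207 | 96 |
| 12% | 0.379 | 62% | 146 | 46 |
| 5% | 0.224 | 78% | 86 | 19 |

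(Effective n uses unrounded ratios.) The loss passes one half only when p is below about 21% or, by symmetry, above about 79%.

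**Check without the normal assumption.** Two groups of 192 with beta-distributed percentages (precision parameter φ), comparing a t-test on the percentage with a two-proportion test at 75%:

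| Mean use, shape | Group difference in mean | Above 75% in each group | Power, full scale | Power, 75% cut | Kept |
|---|---|---|---|---|---|
| 50%, U-shaped (φ = 0.6) | 11 points | 33% and 44% | 0.78 | 0.65 | 70% |
| 30%, U-shaped (φ = 0.6) | 10 points | 16% and 24% | 0.77 | 0.52 | 54% |
| 30%, flatter (φ = 2) | 7.5 points | 6% and 11% | 0.78 | 0.31 | 27% |

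Over all settings where the ratio could be computed, 27% to 70% of the information was kept.

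**What the 75% model can detect.** At 80% power for an evenly split characteristic, the detectable difference in proportions is about (1.96 + 0.84) × √[2p(1 − p)/192]. At p = 0.12 this is 0.093, an odds ratio of about 2.5. At p = 0.50 it is 0.143, an odds ratio of about 1.8.

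**Ordinal alternative.** Simulating six ordered categories with a common odds ratio of 1.6 gives power of 31% to 34% (75% cut) against 70% to 73% (rank test) when 12% exceed the cut, 51% to 52% against 73% to 76% at 25%, and 63% to 64% against 73% to 75% at 50%. The ranges cover different assumed distributions. All of these runs generate exact proportional odds, which favours the ordinal analysis, so they indicate direction rather than a promised gain.

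**The case against.** The strongest defence is that the stated aim is how *concordance* varies with provider characteristics. Concordance is a status, and a logistic model at a named threshold addresses it directly. A fractional or ordinal model targets average use or a pooled odds ratio, which is the same question only if odds are proportional. The protocol does not treat its cuts as interchangeable: 75% stands for good concordance and 25% is there for comparability. Fixing one in advance prevents picking the cut from the data. All of this stands, and it is why the 75% model should not be replaced.

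It is also a secondary analysis, and the primary description keeps both the continuous measure and several cuts. That limits the weight of the point. It does not answer it, because the description says nothing about whether the correlates depend on the cut.

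Section 11.1 says no formal hypothesis testing will be done for the objectives, so power might seem irrelevant. But section 11.3 uses significance to decide which variables enter the model, so sensitivity does matter. A statistical analysis plan could add sensitivity models; here, though, the protocol itself states the outcome definition, so this is a choice made rather than a detail left open.

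A reader might also infer that the plan discards most of the information, citing section 2.1, where general dentists and endodontists are contrasted with pediatric dentists: "general dentists (12%) and endodontists (4%) to employ partial caries removal". The documents do not support that. The 12% is a technique category in another survey, not the share using selective removal at least 75% of the time. Sections 2.2 and 3.1 cite a review in which about half of dentists rejected evidence-based strategies. That is not a figure at the 75% cut either, but it allows a much higher prevalence.

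**Conclusion.** The point holds as a cheap improvement to a secondary analysis. One cut, at the upper end of the protocol's own range, is applied to a measure otherwise treated as continuous, in the section that calls the threshold unagreed. Some information is lost at every prevalence examined: about 36% to 78% as the share above the cut falls from 50% to 5%, under a latent-normal assumption that the beta simulations broadly support. The consequence is a greater chance that the significance screen drops real correlates, and no view of whether the correlates depend on the threshold.

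The size rests on prevalences and shapes that the protocol does not give. A loss of more than half would need fewer than about 21% (or more than 79%) above the cut. Nothing here shows that 75% is a wrong or data-driven definition, or that a different cut would give different correlates; the plan simply would not reveal it if one did.

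**What to change.** In section 11.3:

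- Keep the prespecified logistic model at 75% as the analysis of good concordance.
- Add one prespecified model on the full percentage scale: a fractional logit with robust standard errors, or proportional odds on the ordered percentage. Name which in advance. Fit it to the full candidate list, not only to variables that pass the screen at 75%; otherwise it cannot show what that screen dropped.
- Report the odds ratio for each characteristic at every cut point planned for the descriptive analysis, listing the intermediate cuts between 25% and 75%. This shows directly whether the correlates depend on the threshold, and serves as the informal check of proportional odds.
- Do this for symptomatic and asymptomatic caries, as already planned.

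No new data are needed. The cost is a few sentences of analysis text, additional models to report, and a proportional-odds check if the ordinal model is chosen.
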